6.2 Methods of Minimizing Bias

Unmeasured confounding and bias will be minimized by randomization and objective endpoints.

6.2.1 Randomization

Participants will be randomized to two parallel groups in a 2:1 ratio to receive either rhC1INH (intervention) in addition to standard of care (SOC) or SOC treatment (control). Randomization will be stratified by the study site before inclusion using randomly permuted block sizes of four.

6.2.2 Blinding Procedures

Participants, treating physicians and nurses and Investigators will not be blinded.

6.2.3 Other Methods of Minimizing Bias

Not applicable.

6.3 Unblinding Procedures (Code break)

Not applicable.

7. STUDY POPULATION

Patients admitted for the management of confirmed COVID-19 infection will be approached. If enrollment goals are not met expansion to other centers in the United States will be explored.

7.1 Eligibility Criteria

Participants fulfilling all of the following inclusion criteria are eligible for the study:

- Informed Consent as documented by signature,
- Male or Female age 18-85 years,
- Admitted to the hospital because of confirmed COVID-19 infection (by a positive SARS-CoV-2 PCR result),
- Expected to remain an inpatient over the next four (4) calendar days from time of enrollment,
- Evidence of pulmonary involvement on CT scan or chest X-Ray of the chest (e.g. ground glass opacities),
- Symptom onset within the previous 10 days OR shortness of breath within the previous 5 days. Symptoms include fever or one respiratory symptom (patients presenting later may have already progressed to an inflammatory state that is potentially not amenable to C1INH treatment). Respiratory symptoms include cough, sore throat, hemoptysis, shortness of breath, runny nose, or chest pain and
- at least one additional risk factor for progression to mechanical ventilation: 1) arterial hypertension, 2) >50 years, 3) obesity (BMI>30.0 kg/m²), 4) history of cardiovascular disease, 5) chronic pulmonary disease, 6) chronic renal disease, 7) C-reactive protein of >35mg/L, 8) oxygen saturation at rest in ambient air of <94%. Cardiovascular disease includes a history of coronary artery disease, cerebrovascular disease, peripheral artery disease, rheumatic heart disease, congenital heart disease and of

recent (< 3 months) deep vein thrombosis or pulmonary embolism. Chronic pulmonary disease includes a history of chronic obstructive pulmonary disease, asthma, occupational lung disease, interstitial lung disease or of pulmonary hypertension. Chronic renal disease is defined as a history of an estimated glomerular filtration rate (according to the Chronic Kidney Disease Epidemiology Collaboration equation) < 60ml/min/1.73 m² for at least three months.

*Also refer to the WHO definition for additional Cardiovascular diseases

The presence of any one of the following exclusion criteria will lead to exclusion of the participant:

- Contraindications to the class of drugs under study (C1 esterase inhibitor), e.g. known hypersensitivity or allergy to class of drugs or the investigational product,
- Treatment with tocilizumab or another IL-6R or IL-6 inhibitor (within 24 hours) prior to enrollment,
- History or suspicion of allergy to rabbits,
- Women who are of childbearing potential and not using at least one method of contraception (oral contraceptives, barrier methods, approved contraceptive implant or abstinence) before randomization, after discharge and for the entire follow up study period,
- Women who are pregnant or breast feeding or have a positive serum β-human chorionic gonadotropin (hCG) pregnancy test at screening,
- Active or planned treatment with any other complement inhibitor,
- Chronic Liver Disease (any Child-Pugh score B or C),
- Incapacity or inability to provide informed consent,
- Currently admitted to an ICU or expected admission within the next 24 hours,
- Currently receiving invasive or non-invasive ventilation, (with the exception of high-flow oxygen therapy).
- In the opinion of the treating time, death is deemed to be imminent and inevitable within the next 24 hours,
- Participation in another study with investigational drug within the 30 days preceding and during the present study with the following exemptions:
 - 1) participation in COVID-19 drug trials started at least 48 hours before admission (e.g. postexposure prophylaxis with hydroxychloroquine) and
 - 2) participation in COVID-19 drug trials during ICU admission,
- Any uncontrolled or significant concurrent illness that would put the patient at a greater risk or limit compliance with the study requirements at the discretion of the investigator,
- Previous enrollment into the current study, and
- Enrollment of the Investigator, his/her family members, employees and other dependent persons

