----------------------------------	--

	
uncontrolled complement activation and collateral lung damage and 2) reduce capillary leakage and subsequent pulmonary edema by direct inhibition of KK system.
 
Hypothesis: Administration of rhC1INH for 4 days in addition to standard of care (SOC) in patients hospitalized with non-critical SARS-CoV-2 pneumonia (WHO Ordinal Scale Score 3 or 4) will be associated with a reduced clinical severity on day 7 after inclusion and a lower risk of disease progression to ALI and ARDS.

Objective(s):	
The primary objective of the study is to determine if adding 4 days of treatment with rhC1INH to SOC treatment in adult participants admitted with non-critical COVID-19 will affect disease severity within 7 days after inclusion as assessed by the WHO Ordinal Scale for Clinical Improvement ("WHO Ordinal Scale").
 
Secondary objectives will determine if rhC1INH will
 
 - Reduce the time to clinical improvement (time from randomization to an improvement of two points on the WHO ordinal scale or live discharge from hospital, whichever came first) within 14 days after enrollment. - Increase the proportion of participants alive and not having required invasive or non-invasive ventilation at 14 days after enrollment. - Reduce the proportion of subjects with ARDS (defined by Berlin severity criteria) within 14 days after enrollment.
Outcome(s):	
The primary endpoint will be the disease severity on the 7-point WHO Ordinal scale on day 7. The WHO Ordinal scale measures illness severity over time.
 
Secondary endpoints include:
 
 - Time to clinical improvement (time from randomization to an improvement of two points on the seven-category WHO Ordinal scale or live discharge from hospital, whichever came first) within 14 days after enrollment. - Proportion of participants alive and not having required invasive or non-invasive ventilation at 14 days after enrollment. - Proportion of subjects with ARDS (defined by Berlin severity criteria) within 14 days after enrollment.
Study design:	Randomized, open-label, parallel-group, controlled, multi-center clinical trial

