--	---

	
• Chronic Liver Disease (any Child-Pugh score B or C),• Incapacity or inability to provide informed consent,• Currently admitted to an ICU or expected admission within the next 24 hours,• Currently receiving invasive or non-invasive ventilation (with the exception of high-flow oxygen therapy),• In the opinion of the treating time, death is deemed to be imminent and inevitable within the next 24 hours,• Participation in another study with investigational drug within the 30 days preceding and during the present study with the following exemptions: 1) participation in COVID-19 drug trials started at least 48 hours before admission (e.g. postexposure prophylaxis with hydroxychloroquine) and 2) participation in COVID-19 drug trials during ICU admission,• Any uncontrolled or significant concurrent illness that would put the patient at a greater risk or limit compliance with the study requirements at the discretion of the investigator.• Previous enrollment into the current study, and• Enrollment of the Investigator, his/her family members, employees and other dependent persons
--	--

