5. STUDY OUTCOMES

5.1 Primary Outcome

The primary endpoint will be the disease severity on the 7-point WHO Ordinal Scale on Day 7. This endpoint has been suggested by WHO for clinical trials in patients with COVID-19. The ordinal scale measures illness severity over time.

Figure 2: WHO ordinal scale for clinical improvement.

Patient State	Description	Score
Outpatient	No limitation in activities	1
	Limitation in activities	2
Hospitalized Mild disease	No oxygen therapy	3
	Oxygen by mask or nasal prongs	4
Hospitalized Severe disease	Non-invasive ventilation or high-flow oxygen	5
	Intubation, mechanical ventilation +/- additional organ support	6
Death	Death	7

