5.2 Secondary Outcomes

The secondary endpoints will evaluate the effect of rhC1INH treatment in addition to SOC treatment relative to only SOC treatment on disease progression as measured by

- Time to clinical improvement (time from randomization to an improvement of two points on the seven-category WHO Ordinal Scale or live discharge from hospital, whichever came first) within 14 days after enrollment.
- Proportion of participants alive and not having required invasive or non-invasive ventilation at 14 days after enrollment.
- Number of days hospitalized (per patient)
- Number of days alive (per patient)

- Proportion of subjects with ARDS (defined by Berlin severity criteria) within 14 days after enrollment

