9.1.1 Assessment of primary outcome

For the analysis of the primary endpoint, illness severity will be assessed on each day after enrollment (worst status) with the use of the WHO Ordinal Scale for Clinical Improvement and the score on day 7 will be analyzed stratified by its baseline value.

Patient State	Description	Score
Outpatient	No limitation in activities	1
	Limitation in activities	2
Hospitalized Mild disease	No oxygen therapy	3
	Oxygen by mask or nasal prongs	4
Hospitalized Severe disease	Non-invasive ventilation or high-flow oxygen	5
	Intubation, mechanical ventilation +/- additional organ support	6
Death	Death	7

Figure 3: WHO ordinal scale for clinical improvement.

The worst score on a given day (between 0:00 and 24:00 hours) will be used for the categorization

Patient State	Description	Score
Outpatient	No limitation in activities	1
	Limitation in activities	2
Hospitalized Mild disease	No oxygen therapy	3
	Oxygen by mask or nasal prongs	4
Hospitalized Severe disease	Non-invasive ventilation or high-flow oxygen	5
	Intubation, mechanical ventilation +/- additional organ support	6
Death	Death	7

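### The synopsis hypothesis covers WHO score 3 or 4, but eligibility admits high-flow oxygen (score 5), and the time-to-improvement comparison has no stated handling of baseline score

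*Protocol*

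**What the plan says.** The protocol synopsis states the hypothesis for treatment "in patients hospitalized with non-critical SARS-CoV-2 pneumonia (WHO Ordinal Scale Score 3 or 4"). The exclusion criteria in section 7.1 remove patients on ventilation but carve out one group: "Currently receiving invasive or non-invasive ventilation, (with the exception of high-flow oxygen therapy"). The synopsis lists the same exclusion with the same exception.

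The scale in protocol section 5.1 (repeated in the synopsis and section 9.1.1) defines score 5 as "Non-invasive ventilation or high-flow oxygen" and places it under severe hospitalized disease.

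For the primary endpoint, section 9.1.1 says that "the score on day 7 will be analyzed stratified by its baseline value". Protocol section 11.4.2 and SAP section 14.5.1 specify the matching stratified Wilcoxon test.

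The first-listed secondary endpoint (protocol section 5.2, SAP section 5.1.2) is the time to "improvement of two points on the seven-category WHO Ordinal Scale or live discharge from hospital, whichever came first", within 14 days. Protocol section 11.4.3 and SAP section 14.5.2 provide Kaplan-Meier plots and a Wilcoxon rank test for it, and mention no stratification.

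**The concern.** The hypothesis and the eligibility rule describe different populations. A result could be reported as applying to score 3 or 4 patients when the trial was not restricted to them.

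The mismatch also changes what one endpoint measures. A two-point improvement from score 5 stops at a state in which the patient is still an inpatient. From score 3 or 4 it requires leaving hospital. If score 5 patients enter, the time-to-improvement curves mix two kinds of event. Randomization is stratified by site only (protocol section 6.2.1), so a chance imbalance in score 5 entrants would pass unadjusted into this comparison. The endpoint is one of those formally tested after a significant primary result, so its reading matters.

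**Working it through.** **1. Can a score 5 patient enter?**

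| Source | What it implies for a ward patient on high-flow oxygen |
|---|---|
| Synopsis hypothesis | Outside the population (score 3 or 4 only) |
| Exclusion criteria, synopsis and section 7.1 | Not excluded (explicit exception) |
| Inclusion criteria, section 7.1 | No limit on baseline score |
| ICU exclusion, section 7.1: "Currently admitted to an ICU or expected admission within the next 24 hours" | Narrows the group, but a patient on the ward with no expected ICU transfer stays eligible |
| Scale, section 5.1 | Score 5 |

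The exception appears in both copies of the exclusion list, so it is not a slip in one place. Such a patient is eligible and outside the synopsis hypothesis.

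**2. What does the improvement event mean for each entry score?** Target score = entry score minus 2.

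| Entry score | Target | State at target | Event requires leaving hospital? |
|---|---|---|---|
| 3 | 3 − 2 = 1 | Outpatient, no limitation | Yes |
| 4 | 4 − 2 = 2 | Outpatient, with limitation | Yes |
| 5 | 5 − 2 = 3 | In hospital, no oxygen therapy | No |

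Live discharge also counts as an event. For score 3 and 4 entrants the event therefore reduces to live discharge. For score 5 entrants it is whichever comes first, score 3 in hospital or live discharge. The analysis sections shorten the definition to an improvement of at least 2 points. Under that wording too, score 3 and 4 entrants must leave hospital and score 5 entrants need not.

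**3. How is baseline score handled?** The primary test is stratified by it (protocol 9.1.1 and 11.4.2, SAP 14.5.1). Time to improvement has no stated stratification (protocol 11.4.3, SAP 14.5.2).

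**4. Size.** The plan's total of 120 reproduces and is not in dispute:
- Per group, with effect 1, SD 1.5, two-sided 0.05 and power 0.80: 2 × (1.960 + 0.842)² × 1.5² / 1² = 35.3, so 36.
- Dividing by the Wilcoxon efficiency 3/π: 36 / 0.955 = 37.7, so 38, as stated.
- With the plan's additions: 38 + 4 + 4 = 46 per group, 92 in all.
- For 2:1 allocation: 92 × 9/8 = 103.5.
- With three-look Pocock inflation of 1.166 (equally spaced looks): 103.5 × 1.166 = 120.7, against 120 stated.

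The documents give no expected share of score 5 entrants. Assumed for illustration:
- 10%: 0.10 × 120 = 12 patients, about 8 treated and 4 control at 2:1.
- 20%: 0.20 × 120 = 24 patients, about 16 treated and 8 control.

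**The case against.** The case for leaving the plan alone has substance.

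- **The score limit appears once.** It is a parenthesis in the synopsis. The formal hypotheses in section 11.1 refer to admitted COVID-19 patients with no score limit, and the primary objective in section 4.2 says only non-critical. Score 5 is labelled severe, which is not plainly the same as critical. This stands. It makes the conflict one between the synopsis hypothesis and the eligibility rule, but does not remove it.
- **The endpoint is openly a composite.** A fixed-point improvement always means different states from different starting points, and the same definition applies in both arms. This also stands: no bias between arms is shown. The remaining gap is that baseline score is handled for the primary test and not for this one.
- **The endpoint is secondary in an exploratory pilot.** True, and it limits the weight of the point.

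Three stronger readings are tempting, and the documents do not support them.

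- A reader might infer that the primary analysis is compromised. Its stratification compares score 5 entrants with score 5 entrants, so its validity is not threatened. Only the description of the population to which it applies is affected.
- A reader might infer that the ventilation-free endpoint cannot be told apart from score 5, because score 5 combines non-invasive ventilation and high-flow oxygen. That endpoint is not derived from the scale: section 9.1.2 assesses ventilation and death directly each day to Day 14, and the visit procedures document ventilation separately.
- A reader might infer a loss of power. If only score 3 or 4 patients counted, power would fall from about 84% to about 80% at an assumed 10% share, or 75% at 20% (effect 1, SD 1.5, 10% drop-out, 3/π efficiency, 2:1, equally spaced looks). Neither document plans to discard score 5 patients. The primary analysis set is everyone randomized, so this loss does not arise.

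**Conclusion.** The inconsistency is real and can be read directly from the protocol: the synopsis hypothesis and the exclusion criteria define different populations, and no other criterion closes the gap. Its analytic effect is confined to time to clinical improvement, where the event has a different meaning for score 5 entrants and no baseline stratification is stated.

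The size depends on how many score 5 patients enter. The 12 to 24 of 120 quoted above rests wholly on an assumed 10 to 20% share, and the ICU exclusion may keep the number lower. If none enter, the endpoint problem disappears and only the wording conflict remains. Which eligibility rule is right is a clinical choice on which this review takes no position.

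**What to change.** State the allowed baseline WHO scores once, and use the same statement in the synopsis hypothesis, the objectives and the eligibility criteria.

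If score 5 entrants remain eligible, amend protocol section 11.4.3 and SAP section 14.5.2 so that the time-to-improvement test is stratified by baseline WHO score, as the primary test already is. Present the results descriptively by baseline score as well, with a note that the score 5 group would be small and imprecise (about 4 to 8 controls under the illustrative share).

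The cost is protocol and SAP wording and one additional table. Baseline score is already recorded at Day 0, so no new data are needed and the sample size is unaffected.

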7.2 Recruitment and Screening

Patients who are admitted to the hospital for treatment of confirmed COVID-19 infection will be screened after results from history (symptom onset) and routine investigations (including a CT scan or Chest X-Ray of the chest) if available. Patients that at least fulfil the age, CT or chest x-ray criteria and reason for admission will be approached by study staff to explain the study, verify inclusion/exclusion criteria and obtain informed consent prior to enrollment.

7.3 Assignment to Study Groups

Following study enrollment, an Investigator or study nurse will determine treatment allocation via the randomization list. Subsequently, rhC1INH will be prepared and supplied by the local pharmacy to the Investigator or study nurse for administration in the active treatment group.

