2.5 Patient Information and Informed Consent

The Investigators will explain to each participant the nature of the study, its purpose, the procedures involved, the expected duration, the potential risks and benefits and any discomfort it may entail. Each participant will be informed that the *participation in the study is voluntary and that he/she may withdraw from the study at any time and that withdrawal of consent will not affect his/her subsequent medical assistance and treatment*.

The participant must be informed that his/her medical records may be examined by authorized individuals other than their treating physician.

All participants for the study will be provided a participant information sheet and a consent form describing the study and providing sufficient information for participant to make an informed decision about their participation in the study. Participants will have at least two hours and the opportunity to ask questions in order to decide on their participation. In the event that Informed Consent (IC) is obtained on the date that any study procedures are performed, the study record or subject's clinical record will clearly show that IC was obtained prior to these procedures.

Due to the special situation in SARS-CoV-2 infected patients including physical isolation, consent will be obtained in two possible ways (in accordance with the *FDA Guidance on Conduct of Clinical Trials of Medical Products during COVID-19 Public Health Emergency Guidance for Industry, Investigators, and Institutional Review Boards*):

Method 1: A photograph of the signed informed consent document can be transmitted to the trial staff

1. An unsigned consent form is provided to the patient by a person who has entered the room.
2. The Investigator/designee arranges a telephone call or video conference call with the patient (and, if desired and feasible, additional individuals requested by the patient (e.g., next of kin)).
3. To ensure that patients are approached in a consistent fashion, a standard process should be used that will accomplish the following:

- Identification of who is on the call.
- Review of the informed consent document with the patient by the Investigator/designee and response to any questions the patient may have.
- Verbal confirmation by the patient that their questions have been answered that they would like to participate in the trial, and that they have signed and dated the informed consent document that is in their possession.

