7.4 Criteria for Withdrawal / Discontinuation of Participants

Subjects may voluntarily withdraw from study participation at any time without having to provide a reason. Subjects may be withdrawn because of the appearance of a new health condition requiring care or medications prohibited by the protocol, unacceptable adverse event, refusal to continue treatment, or at the Investigator's discretion if it is in the subject's best interest.

A subject who withdraws informed consent before randomization or who develops a violation of the selection criteria before randomization is defined as a screening failure. No follow-up of screening failures will be performed.

Participants who withdraw informed consent, who do not fulfil inclusion/exclusion criteria after obtaining informed consent or who are diagnosed with an alternative disease (e.g. influenza infection) AND have not received any study medication will be withdrawn from the study.

Participants who experience a type I allergic reaction after any dose of study medication will be discontinued from further study interventions. Withdrawn or discontinued participants will not be replaced. Follow-up for all patient groups will be explained in [Section 8.5](#).

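### Site staff obtain the allocation from a randomisation list, and neither document says that upcoming entries are concealed from those who screen, consent and enrol in this open-label trial

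*Protocol*

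**What the plan says.** **Who obtains the allocation.** Protocol Section 7.3: "Following study enrollment, an Investigator or study nurse will determine treatment allocation via the randomization list". The local pharmacy prepares the drug after that.

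**Who brings patients in.** Under Section 7.2, candidate patients are "approached by study staff to explain the study, verify inclusion/exclusion criteria and obtain informed consent prior to enrollment". The consent procedure in Section 2.5 includes "Review of the informed consent document with the patient by the Investigator/designee and response to any questions the patient may have".

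**How the sequence is built.** Section 6.2.1: "Participants will be randomized to two parallel groups in a 2:1 ratio". It then adds: "Randomization will be stratified by the study site before inclusion using randomly permuted block sizes of four". Section 11.2 and SAP Section 6 give 80 + 40 patients. The SAP does not describe an allocation mechanism.

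**Blinding and other safeguards.** Section 6.2.2: "Participants, treating physicians and nurses and Investigators will not be blinded". Section 6.2: "Unmeasured confounding and bias will be minimized by randomization and objective endpoints". Section 6.2.3, on other methods of minimising bias, is marked not applicable.

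**Between enrolment and randomisation.** Section 9.2.1 places consent, the eligibility check and enrolment at Visit 1 (Day -1) and randomisation at Visit 2 (Day 0). Under Section 7.4, a subject who "develops a violation of the selection criteria before randomization is defined as a screening failure. No follow-up of screening failures will be performed". The FAS/ITT set (Section 11.4.1) holds randomised patients only.

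**The concern.** Randomisation protects against selection only if whoever decides that a patient enters cannot know or guess the arm that comes next. As written, the procedure puts the list in use at the site, among unblinded staff, and no sentence separates the list from recruitment.

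The eligibility criteria leave room to act on such knowledge. The expected four-day stay, ICU admission expected within 24 hours, and significant concurrent illness at the investigator's discretion (Section 7.1) are all judgements. A patient can be deferred, not approached, or declared a screening failure between Day -1 and Day 0. A screening failure is not followed up and never enters the FAS/ITT set, so analysis by allocated arm cannot correct for the loss. Stratifying the Wilcoxon test by baseline WHO score balances the score level but not prognosis within a level.

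The trial also has little else to rely on. Section 6.2 names two protections, and the second is partial: the scale levels turn on discharge and oxygen-support decisions made by staff who know the arm.

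**Working it through.** **Inputs.** Block size four, ratio 2:1, strata = sites (Section 6.2.1); 80 + 40 patients and SD 1.5 (Section 11.2); 4 to 10 sites (Section 1.5; Section 6.1 says five to ten). The documents give no predictability figure to reproduce.

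**Step 1. Does a block of four give 2:1?** 4 × 2/3 = 2.67, so no single block of four can. With 120/4 = 30 blocks:
- all 3:1 gives 90/30;
- all 2:2 gives 60/60;
- 20 blocks of 3:1 and 10 of 2:2 give 60 + 20 = 80 active and 20 + 20 = 40 control.

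Only the last reaches the stated split, and the documents do not describe it.

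**Step 2. How many allocations are certain from earlier ones?** Because strata are sites and nobody is blinded, site staff can count their own patients and know where each block starts. An allocation is certain when the allocations already made in its block leave only one possible arm.
- *All 3:1.* The single control is equally likely in positions 1 to 4, which leaves 3, 2, 1 or 1 certain allocations. Mean 7/4 per block; 7/16 = 43.8%.
- *All 2:2.* Of six sequences, two leave 2 certain allocations and four leave 1. Mean 8/6 per block; 8/24 = 33.3%.
- *Mix, composition of each block unknown to the site.* Three actives in a row (probability 2/3 × 1/4 = 1/6) make the fourth certain. Each 2:2 sequence has probability 1/3 × 1/6 = 1/18. Two controls first leaves 2 certain allocations, contributing 2/18. The two orders with the second control in third place leave 1 each, contributing 2/18. Total 1/6 + 4/18 = 7/18 per block; 7/72 = 9.7%.

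| Situation | Split of 120 | Certain in advance | Best guess correct |
|---|---|---|---|
| Future list entries visible | any | 100% | 100% |
| Hidden, all 3:1 | 90/30 | 43.8% | 81.3% |
| Hidden, all 2:2 | 60/60 | 33.3% | 70.8% |
| Hidden, 3:1 and 2:2 mix | 80/40 | 9.7% | 72.2% |

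For a true 2:1 ratio, always naming the active arm is right 66.7% of the time. With 120/10 = 12 to 120/4 = 30 patients per site, the pattern recurs over 3 to 7.5 blocks per site.

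**Step 3. Illustration of the effect on type I error (steering is assumed).** The SE of the mean difference is 1.5 × √(1/80 + 1/40) = 0.290. Suppose 10%, 20% or 30% of enrolments are steered, with a 1-point prognostic difference. The arms then differ by 0.1, 0.2 or 0.3 points under no effect, z shifts by 0.34, 0.69 or 1.03, and a fixed two-sided 5% test rejects in 6.4%, 10.6% or 17.8% of null trials.

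A simulation of an unstratified Wilcoxon test (120 patients, 6 sites of 20, SD 1.5, 2,000 runs per cell) assumed that staff shift prognosis by 0.15, 0.3 or 0.5 points each way:

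| Staff act on | 0.15 | 0.3 | 0.5 |
|---|---|---|---|
| Visible list (3:1 blocks) | 14% | 43% | 85% |
| Certain allocations only, 3:1 | 7% | 11% | 19% |
| Certain allocations only, 2:2 | 6% | 11% | 22% |
| Certain allocations only, mix | 5% | 5% | 6% |

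**Step 4. What would hidden blocks that fit 2:1 give?** With undisclosed blocks of 3, 6 and 9 in random order (4,000 simulated runs), about 3.4% of allocations are certain and the best guess is right 73.4% of the time. A fixed, known block of six (4:2) still leaves 28.9% certain. Concealing the list therefore matters more than the choice of block size.

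**The case against.** The strongest reply is that the protocol is silent on list custody but does not permit foreknowledge. A reader might infer that the person who enrols is the person who reads the list, and that the list shows future entries. The documents say neither. Section 7.2 speaks of study staff and Section 7.3 of an investigator or study nurse; the overlap is likely but inferred. Section 7.3 also puts allocation after enrolment, and the list might be consulted through a concealed system that is not described. This stands as a limit on the claim: foreknowledge is possible, not shown. It does not remove the gap, because enrol-then-allocate protects only if the next entry is hidden.

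A reader might also take 33% to 44% as the predictability of this trial. Those figures need all-2:2 or all-3:1 blocks, which give 60/60 or 90/30. Under the one mix that gives 80/40, certainty falls to about 10%, and steering on certain allocations alone barely moves the type I error. In that case the 30% steering scenario could not be reached from certain allocations only. Block predictability is thus the secondary part of the point.

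The type I error figures use invented steering and an unstratified test at a fixed 5% level. The plan has a baseline-stratified test with inverse-normal combination at 0.0221.

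Two apparent supports should be set aside. Section 6.3 is marked not applicable, but it concerns code break and says nothing about concealment. The sealed boxes in Section 8.1.1 are drug supplies opened after randomisation; they neither hide nor reveal the sequence.

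Finally, SAP Section 14.11 already lists screened subjects who were not eligible, with the reason. That covers part of the audit trail, but not consented patients who were not randomised for other reasons, and not the time of the decision.

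**Conclusion.** The point holds in this form: Section 7.3 has site staff obtain allocations from a list, and nothing in either document conceals that list from those who recruit, in an open-label, site-stratified trial with a published block size. It should be fixed even in an exploratory pilot, because randomisation is one of only two named protections against bias and selection before randomisation cannot be undone in the analysis.

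The size is conditional. If future entries are visible, 100% of upcoming allocations are known. If they are hidden, about 10% to 44% are certain from earlier ones, depending on a block composition that the protocol does not state. This assumes that staff know the block size and track their site's allocations and, for the single-composition cases, know the composition. The documents do not show that any steering would occur, so they support no specific type I error rate. The mismatch between blocks of four and 2:1 is a separate error in Section 6.2.1 that needs correcting in any case.

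**What to change.** 1. **Protocol Section 7.3.** State that allocation is released for one patient at a time, after signed consent, confirmed eligibility and the baseline WHO score have been logged. The release comes from the EDC system (Section 12.1.4), or from a pharmacy or CRO that holds the list. State that investigators and study nurses have no access to the list. The documents do not say whether the EDC has a randomisation function, and SAP Section 7 describes double entry of CRFs; if it has none, use the pharmacy or CRO route. If a concealed procedure already exists, write it in.
2. **Protocol Section 6.2.1.** Replace the block size of four with randomly varying sizes in multiples of three (for example 3, 6 and 9), known only to whoever generates the list. Varying sizes alone are not enough: sizes that are not multiples of three would again fail to hold 2:1.
3. **SAP Section 14.11.** Extend the existing listing to every consented patient who is not randomised, with date, time and reason.

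The cost is protocol and SAP wording, set-up of the release step, and a few minutes per randomisation, with no extra patients. An unfinished block at a small site can leave that site slightly off 2:1, which is a minor price.
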